## **Abstract**

---

Many obstetrical interventions used in Latin America, as in other parts of the world, have been shown to be ineffective or harmful, while effective interventions remain underutilized. The goal of this project is to develop and evaluate an intervention intended to implement evidence-based practices among birth attendants in Latin America.

The aim of this project is to perform a cluster randomized controlled trial of a behavioral intervention in Argentina and Uruguay that will increase the use of two evidence-based birth practices, the selective use of episiotomies and active management of the third stage of labor. The intervention will be based on the stages of change and organizational change theories and tailored by formative research that will include baseline questionnaires and focus groups.

Twenty-four hospitals in three urban districts of Argentina and Uruguay will be randomized. Opinion leaders in the 12 intervention hospitals will be identified and trained to develop evidence-based guidelines. They will then diffuse the guidelines by using a multifaceted approach including seminars, academic detailing, reminders, and feedback on utilization rates. The 12 hospitals in the nonintervention group will continue with their standard in-service training activities. The main outcomes to be assessed are the use of episiotomies and of oxytocin during the third stage of labor. Secondary outcomes will be perineal sutures, postpartum hemorrhages, and birth attendants' opinions.

The Latin American Center for Perinatology (CLAP) will be the coordinating center for the trial. In this way, the project endeavors to facilitate capacity building of CLAP and its network of hospitals to perform studies integrating behavioral and clinical research methods. It is also anticipated that the project will contribute to the Global Network by increasing access to a large number of Latin American hospitals that have the capacity to participate in multicentric randomized controlled trials and other clinical studies.

## 1. Study Objectives and Significance

---

### *1.1. Statement of the Problem*

The evaluation of the medical care in general and of the area of perinatology in particular, shows alarming results. It has been seen that only 15% of the health related practices are based on valid scientific evidence. This situation is even more serious in Latin American countries, where a significant proportion of the care administered to women during the prenatal period, delivery, and the postpartum are scientifically verified as ineffective or harmful.

For example, Belizán et al. (1999), estimated that 12 of the 19 Latin American countries they examined had cesarean section rates above the maximum 15% rate recommended by the World Health Organization (WHO). They calculated that around 850,000 unnecessary cesarean sections are performed each year in the Latin American region. Additionally, many other obstetrical interventions used in Latin America, as in other parts of the world, are not evidence based.

Another practice that follows the same pattern is routine use of episiotomy a practice demonstrated as useless and even harmful (Carroli and Belizán, 2000). We studied the use of episiotomy in 41 hospitals in Latin America between 1990 and 1998. The range of episiotomy rates in vaginal births of nulliparous women is between 49.3% and 98.3%, the median rate is 91.3%, and the mean value is 88.4% (Althabe et al., 2002). From these figures, we can conclude that every 10 women giving birth vaginally for the first time, 9 are currently receiving an episiotomy. Simultaneously, many of the practices verified as beneficial are not routinely used. For example, the management of the third stage of labor has been proven to be beneficial for the prevention of postpartum hemorrhage. (Prendiville et al., 2000). However, a survey in 19 maternity services of Montevideo, Rosario, and Province of Buenos Aires showed that in 17 of them (89.5%), expectant management was the standard form of care.

Support during labor and delivery that is proven to be beneficial and with no undesirable effects was used in only 21% of women in the survey of the 19 hospitals mentioned above (Althabe and Belizan, 2001).

Although we have no figures, the administration of enemas at admission in labor, perineal shaving, and systematic intravenous infusion are other examples of practices not supported by scientific evidence that are still used in a wide proportion of Latin American hospitals. External cephalic version at term is another example of an evidence-based practice that is not used in Latin American hospitals.

### *The barriers to change*

Why, despite scientific evidence and dissemination efforts are harmful and/or unnecessary procedures still used, while other beneficial procedures are ignored?

What are the bridges and barriers between practice guidelines based on research findings and practitioners? As a wide variety of barriers can hinder practitioners from adhering to

evidence-based practices, a theoretical framework could help explain these barriers and possibly help target interventions to specific barriers. Cabana et al. published a comprehensive systematic review about the barriers to physician adherence to practice guidelines and developed a theoretical approach to the barriers (Cabana et al., 1999).

They review 76 articles which include 5 qualitative studies and 120 different surveys asking questions regarding possible barriers to guideline adherence. Barriers could be classified into seven general categories: the barriers affecting physician knowledge (lack of awareness and lack of familiarity); those affecting attitudes (lack of agreement, lack of self-efficacy, lack of outcome expectancy and the inertia of previous practices); and those affecting behavior (external barriers).

One survey included in Cabana's review is related to the perinatal field and consisted in a survey of 38 childbirth-related organizations regarding the use of the text *Effective Care in Pregnancy and Childbirth* (Lomas, 1993). One of the aspects covered by the survey was the perception of which were the main barriers to effective research transfer. All organizations cited especially the practitioners' failure to keep up with the literature, the lack of resources, and the absence of appreciation for research information as major obstructions for implementation of research findings.

There is not much information regarding this issue in Latin American countries. At least in some countries, there is an active distrust towards change. In a recent study carried out in Argentina, for example, health workers expressed resistance and anger towards top-down programs that were imposed upon them (Pittman et al., 1998). This resentment builds on dissatisfaction with working conditions. In the same study, physicians linked their resistance to new programs to the drop in salary levels and the loss in the social status of their profession. As such, they saw themselves as victims of an unfair situation.

There is no relevant evidence that quantifies the relative weight of each one of the categories of barriers, mainly because most of the studies were done focusing on some of the barriers and not all of them. It is probable that the relative weight varies according to the specialty, specific problem addressed, and setting. We think that the differences among countries are referred to the relative weight of categories, more than to the existence of other general types of barriers.

## ***1.2. Background***

### *1.2.1. Interventions to change professional practice*

Several trials have been performed in North America and Europe to evaluate strategies to change behaviors of birth attendants. Lomas et al. (1991) conducted a trial in Canada with 76 physicians to test three interventions to increase the number of vaginal births after C-section. The interventions compared were (1) distribution of educational materials, (2) local opinion leaders and distribution of educational materials, and (3) audit and feedback and distribution of educational materials. The use of opinion leaders was significantly more effective than audit and feedback and than educational materials alone in increasing the number of women offered a trial of labor and increasing the number of vaginal births.

Another trial performed in Canada (Hodnett et al., 1996) compared a strategy based on the influence of nurse opinion leaders to no intervention. It was hypothesized that the strategy would result in lower rates of epidural analgesia through increasing the amount of support nurses provided to their patients. Other outcomes included rates of narcotic analgesia, episiotomy, and operative delivery. The results showed that the strategy was unsuccessful in improving intrapartum nursing care. The individual marketing approach used in the intervention de-emphasized information about research and did not include institutional changes. The authors suggested that this might partly explain the lack of success of the intervention.

One trial comparing the introduction of a database of systematic reviews, the Cochrane Pregnancy & Childbirth Database, with a control group has been conducted recently (Wyatt et al., 1998). This trial has compared the introduction of the Cochrane database through a single educational visit (outreach visit) conducted by an expert obstetrician with a control group that did not receive any intervention. The educational visit involved meeting with the lead obstetrician and nurse of the labor ward and demonstrating how to select and interpret Cochrane reviews. Twenty-five obstetric units within a small geographic area in England were included in this trial. There was a significant increase in the use of only one of the four recommended practices (vacuum extraction). However, this trial has been conducted in a region where awareness of evidence-based medicine and Cochrane reviews increased significantly during the trial period in both the study and control hospitals, reducing the magnitude of any possible impact of the intervention.

Another cluster randomized trial performed in the United States evaluated the effect of an “active dissemination” strategy compared to a “usual dissemination” strategy, on the use of corticosteroids for fetal lung maturation prior to a preterm birth in 27 hospitals (Leviton et al., 1999). The active strategy consisted of the use of a local opinion leader, grand round lectures given by respected national experts, chart reminders, group interactive discussions, and audit and feed back. In usual dissemination hospitals, the use of corticosteroids increased from 33% to 58% or by 75% over baseline. The active dissemination hospitals increased from 33% to 68% or by 108% over baseline.

Very few trials of a similar nature have been performed in developing countries, and the results of the few that have been performed are inconclusive. Two trials utilizing educational outreach visits were conducted in Indonesia. Santoso et al. (1996) compared two interventions (outreach visits or a formal seminar) to a nonintervention control to improve drug use in the management of acute diarrhea in children. They reported that outreach visits resulted in a significant 24% relative reduction in antimicrobial use compared with the control group. There was a significant 40% relative reduction in the use of antidiarrheals compared to the control group. The authors also reported that the seminar resulted in significantly greater changes from the baseline period than did the outreach group. The use of oral rehydration agents was not significantly improved after either intervention (9% reduction). Ross-Degnan and colleagues (Ross-Degnan et al., 1996) reported that outreach visits to pharmacists/owners, coupled with a small group session with counter attendants, significantly increased sales of oral hydration salts by 40% and reduced antidiarrheal sales by 35% for the treatment of diarrhea.

In sum, multiple strategies to change medical behaviors have been used, with various degrees of success. Few trials have been done in obstetrical settings or in developing countries.

To our knowledge, no randomized controlled trial has been performed to evaluate the effectiveness of an intervention to implement evidence-based birth practices in Latin American countries.

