###### 4.3.2.1.2. *Delivering of information to hospitals*

Hospitals may differ by the level of contact that their staff have with evidence-based literature, although CLAP is providing such information to Latin American obstetric departments on routine basis. In order to insure that hospitals received the same level of previous information from CLAP, heads of the obstetric departments will receive copies of CLAP's newsletters and publications from the past 2 years, and a copy of the WHO Reproductive Health Library (RHL). The presentation of the study to the authorities of preselected hospitals, and the delivering of the bulletins and the RHL will be done in a general presentation meeting to hospital authorities, and in meetings at each participating hospital during the preparation phase.

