### ***10.3. Sample Size***

A preliminary analysis of 1995-98 PIS data from 22 Argentinean hospitals showed a baseline frequency of episiotomies among vaginal deliveries of 42%, with a standard deviation of 11%. To protect against changes in the standard deviation (Lomas et al., 1991), we have based our sample size calculations on a standard deviation of 15%. Thus, we will need 18 hospitals (9 intervention and 9 control) to identify a decrease of episiotomy rates from 40% to 20%, with a 0.05 significance level and a 80% power. Our previous analyses of PIS data have shown that about 25% of deliveries are among primiparae, and 75% among multiparae. A reduction of the general episiotomy rate from 40% to 20% could be achieved by reducing the rate among primiparae from 80% to 40%, and the rate among multiparae from 26% to 13%. The rates after the intervention would be similar to the rates achieved in a previous trial (Argentine Episiotomy Trial Collaboration Group, 1993) and are thus potentially attainable. However, the sample size of 18 hospitals will allow us to identify a smaller decrease of episiotomy rates among primiparae vaginal deliveries, from 80% to 60%, with a 0.05 significance level and a 80% power. Assuming a baseline frequency of perineal sutures among primiparae of 85% with a standard deviation of 15%, our sample size of 18 hospitals will give us a power of 80% to identify a reduction of frequency of perineal sutures to 65%, with a 0.05 significance level.

We expect the use of oxytocin during the third stage of labor to increase from 10% to 50%. However, our sample size will allow us to detect smaller changes. Assuming a baseline frequency of injections of oxytocin of 10% and a standard deviation of 5%, the sample size of 18 hospitals will give us a power higher than 95% to identify an increase of use of oxytocin from 10% to 20%, with a 0.05 significance level. Assuming a baseline PPH incidence rate of 15% and a standard deviation of 5%, the sample size of 18 hospitals will give us a power of

84% to identify a reduction from 15% to 8%, and a power of 56% if the reduction were from 15% to 10%.

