#### ***10.5. Analysis of Primary and Secondary Hypotheses***

At the group level, the primary outcome variable is the percentage of primary and secondary outcomes during the three months following the end of the intervention. Despite having only 12 observations in each arm, since each percentage is based on a large number of births, one can use the Normal approximation to the Binomial distribution, and thus the individual percentages can be assumed to be Normally distributed. This implies that when evaluating the efficacy of the intervention using the mean percentages at the end of the intervention period, the Student's t-test is appropriate and its use is justified. Baseline frequencies will also be presented, and baseline to follow-up ratios will be computed. Mantel Haenszel summary risk ratios combining the individual ratios for each hospital in the intervention group and non-intervention group will be computed. The intervention and non-intervention groups will then be compared at the group level using Student's t-test on the logarithms of the summary risk ratio (Wyatt et al., 1998).

In addition, the data collected at the individual level will be used to explore the potential for confounding of the main effects of the intervention due to imbalances arising from the group randomization. Such multi-level analyses will use mixed model techniques (Littell et al., 1996), also known as hierarchical linear models (Bryk and Raudenbush, 1992). These models account for the clustering effect and the intra-hospital correlation of the women from a given hospital. Furthermore, we will use descriptive statistics and GEE modeling (Diggle et al., 1994) to study the evolution of frequencies of outcomes between the four data collection periods.

For the analysis of provider's "readiness to change", the analysis will include three variables, one assessing "readiness to change" episiotomy, one assessing "readiness to change" management of third stage of labor and one assessing attitude toward changing practice in general. Ordinal scales will be used for the responses. Data will be summarized in terms of medians and interquartile ranges. Non-parametric statistics will be used to compare the pre- and post-intervention differences between the control and intervention groups."

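### The 80% power for episiotomy in section 10.3 assumes, without saying so, that control hospitals stay at 40%, and it is a normal-approximation figure; the planned t-test gives 76% with 9 hospitals per arm

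*Protocol*

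**What the plan says.** - **Sample size (protocol 10.3).** The calculation is "Thus, we will need 18 hospitals (9 intervention and 9 control) to identify a decrease of episiotomy rates from 40% to 20" percent, at a 0.05 significance level and 80% power. It notes an observed between-hospital SD of 11% in 22 hospitals, but "we have based our sample size calculations on a standard deviation of 15" percent as protection. For oxytocin it gives "a power higher than 95% to identify an increase of use of oxytocin from 10% to 20" percent at SD 5%, as an illustration of a change smaller than the expected 10% to 50%. No rate for control hospitals at follow-up is given.
- **Reserve (10.3).** 24 hospitals start baseline collection, to cover drop-outs and exclusions.
- **Test (10.5).** Student's t-test is used "when evaluating the efficacy of the intervention using the mean percentages at the end of the intervention period". A second t-test compares the arms on logarithms of baseline-to-follow-up risk ratios.
- **Timing (5.2).** Data periods are one year apart, so Periods I and III are two years apart.
- **Background (1.2.1).** In a 27-hospital cluster trial of opinion leaders, lectures, reminders, discussions and feedback, "In usual dissemination hospitals, the use of corticosteroids increased from 33% to 58% or by 75% over baseline"; the active hospitals went from 33% to 68%. In a second obstetric trial, awareness of evidence-based medicine "increased significantly during the trial period in both the study and control hospitals, reducing the magnitude of any possible impact of the intervention".
- **Information to all hospitals (4.3.2.1.2).** Before randomization, heads of obstetric departments receive two years of newsletters and publications "and a copy of the WHO Reproductive Health Library (RHL").

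**The concern.** A fall from 40% to 20% in the intervention hospitals is a 20-point difference between the arms only if the control hospitals do not change. Section 10.3 uses the full 20 points as the between-arm difference and does not say that it assumes a stationary control arm. The protocol's own literature review contains a closely similar trial in which controls made much of the improvement, and another in which rising awareness in both arms is said to have reduced the possible effect.

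What is at stake is how the result is read. Suppose the intervention hospitals reach 20% but the controls also improve. A non-significant comparison would then be interpreted against a stated 80% power that did not apply to the difference actually present. The printed figure is also slightly optimistic with no control change at all, because it does not come from the test that section 10.5 names.

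**Working it through.** **Inputs.** From 10.3: difference 40 − 20 = 20 points; SD 15% (planning) and 11% (observed); 9 hospitals per arm, with up to 12 per arm if all 24 are randomized; alpha 0.05, taken as two-sided because that reproduces the plan's number. From 10.5: Student's t-test on hospital percentages. Control falls of 5 and 10 points are assumptions; the protocol gives no figure for these hospitals.

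**1. Reproduce the plan.** Normal approximation, hospital as unit:

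n per arm = 2 × SD² × (1.960 + 0.842)² / difference² = 2 × 225 × 7.85 / 400 = 8.8, so 9.

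The standard error with 9 per arm is 15 × √(2/9) = 7.07. Then 20 / 7.07 = 2.83, and power = Φ(2.83 − 1.96) = 81%. The same method gives 99% for oxytocin 10% to 20%, and 84% and 56% for the two hemorrhage scenarios, all as stated in 10.3. So the plan used a two-sample normal approximation in which the whole change from baseline is the between-arm difference, i.e. no change in controls.

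**2. Use the planned test.** Power from the noncentral t with 2n − 2 degrees of freedom and noncentrality difference / (SD × √(2/n)).

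- 9 per arm, SD 15%: noncentrality 2.83, 16 df, critical value 2.12; power 76%.
- 12 per arm, SD 15%: 20 / 6.12 = 3.27, 22 df, critical value 2.07; power 88%.
- Smallest difference with 80% power at SD 15%: 21.1 points (9 per arm) and 18.0 points (12 per arm). The normal approximation gives 19.8 and 17.2.

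**3. Let the controls move.** The intervention arm reaches exactly 20%, so the between-arm difference is 20 minus the control fall. Two-sided t-test power:

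| Assumed control fall | Control rate at Period III | Difference | SD 15%, 9 per arm | SD 15%, 12 per arm | SD 11%, 9 per arm | SD 11%, 12 per arm |
|---|---|---|---|---|---|---|
| 0 points | 40% | 20 | 76% | 88% | 95% | 99% |
| 5 points | 35% | 15 | 51% | 65% | 78% | 89% |
| 10 points | 30% | 10 | 27% | 35% | 44% | 57% |

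At SD 11% the smallest difference with 80% power is 15.5 points (9 per arm) or 13.2 (12 per arm). The design then absorbs about 4.5 or 6.8 points of control improvement. At SD 15% it absorbs none with 9 per arm and about 2 points with 12.

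**4. The cited trial.** Controls 58 − 33 = 25 points; active 68 − 33 = 35 points; net 68 − 58 = 10 points. Controls made 25/35 = 71% of the active arm's change. This shows that a stationary control arm should not be taken for granted. It does not predict the drift here.

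**5. Oxytocin.** For the expected 10% to 50% at SD 5%, even a 71% control share leaves 40 × 10/35 = 11.4 points, with t-test power above 99% at 9 per arm.

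**The case against.** The strongest reply is that the powers in 10.3 are not miscalculated. They come from a two-sample formula with 9 intervention and 9 control hospitals, and are right, to the accuracy of the normal approximation, for true between-arm differences of 20 and 10 points. The phrase about 40% and 20% can even be read as control against intervention at the end. This stands. A reader might infer that the stated powers belong to a before-after change in one arm; the reproduction in step 1 shows that they do not. What is left is an unstated assumption about the control rate.

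Second, nothing in the documents shows drift in these hospitals. Section 4.5 gives controls no intervention after randomization, and section 1.1 describes entrenched routine practice. The corticosteroid trial concerned another practice in another country, with a usual-dissemination comparator. The second trial is cited for awareness, without control practice rates. The newsletters and library are meant to equalize prior information and are delivered before randomization. So a reader should not infer that the trial will probably miss a real effect. The drift is unknown, the planning SD is deliberately above the observed 11%, and up to 12 hospitals per arm may be available.

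Third, oxytocin. A reader might extend the point to that outcome. The 10% to 20% case is only an illustration of a small change; the expected change keeps ample power at SD 5%.

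Fourth, 33% to 68% is growth of 106%, where section 1.2.1 prints 108%. This is no error: rates that round to 33% and 68% allow growth from about 101% to 111%.

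Finally, 10.5 also tests log ratios to baseline, and the powers above do not describe that comparison. True, but 10.3 is computed on percentages, and the log-ratio test is also between arms, so it too depends on how controls change.

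**Conclusion.** The point holds for episiotomy, as an unstated assumption and a figure from a different calculation than the planned test. The 80% requires control hospitals to remain at 40% at Period III; the protocol does not say so, and its own cited trial gives reason to doubt it. Even with no control change, the planned t-test at SD 15% has 76% power with 9 hospitals per arm, against the stated 80%; with 12 per arm it has 88%.

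The sensitivity to control change depends on the SD. A 5-point control fall gives 51% or 65% at SD 15% but 78% or 89% at SD 11% (9 or 12 per arm). A 10-point fall leaves power below 60% in every case shown. These results rest on a two-sided 5% test, equal arms, the same SD in both arms at follow-up, and control falls that are assumptions. The design itself is not shown to be inadequate.

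**What to change.** In section 10.3:

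1. Express the episiotomy effect as the difference between arms in Period III percentages, and state the control rate assumed at that time.
2. Replace the normal-approximation power by the power of the planned t-test, for 9 and 12 hospitals per arm.
3. Print that power for control falls of 0, 5 and 10 points at SD 15% and SD 11% (the table above), labelled as assumptions.
4. Give the smallest between-arm difference with 80% power: about 21 points with 9 per arm and 18 with 12 at SD 15%.

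The cost is a few sentences and one small table. The 9-per-arm power becomes a little less favourable. Enrolment, conduct and the number of hospitals do not change.
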